11.4. Unforeseeable serious adverse events

SAEs which are not included in section 11.3 are regarded as unforeseeable. Unforeseeable SAEs which occur from randomisation until the first routine follow-up visit must be reported.

11.5. Reporting procedures for serious adverse events

Unforeseeable SAEs and the SAEs associated with frenotomy (section 11.3) must be reported immediately as soon as study staff become aware of the event. Study staff may use one of the following methods:

- Staff with access to the clinical database may report SAEs through this. Once the SAE form is
 complete site staff will be required to print off the clinical database SAE form and obtain the
 signature of the study clinician carrying out the causality assessment. The completed signed SAE
 form must be emailed or faxed to the NPEU CTU. NPEU CTU staff will be informed via email of
 any SAEs reported electronically.
- Emailing or faxing a completed paper SAE form to NPEU CTU. Paper forms, with instructions, will be made available with the trial documentation to enable anyone to report an SAE.
- Where the above routes are not possible, then the SAE may be reported to NPEU CTU by telephone
 and the SAE form will be completed by NPEU CTU staff and a copy shared with the site Principal
 Investigator (PI) for causality assessment.

If following the reporting of an SAE additional information becomes available, a new SAE form should be completed with the details and emailed/faxed to NPEU CTU.

SAEs will be reported from trial entry until the first routine follow-up visit (approximately one week post-intervention according to hospital practice).

The NPEU CTU will forward a copy of the SAE form to the Chief Investigator (CI) or their delegate as soon as possible on receipt. The CI will assess whether the SAE was as a result of trial related activities (related). If assessed to be related and unforeseeable the NPEU CTU will send the SAE report to the Sponsor and the DMC. In addition, all related unforeseeable SAEs should be submitted to the Research Ethics Committee (REC) that gave a favourable opinion of the study within 15 working days of the CI becoming aware of the event, using the HRA report of serious adverse event form (see HRA website).

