- Breastfeeding support workers: Follow-up breastfeeding support outside the hospital frenotomy clinic should be provided by different staff from those conducting the initial assessment of infants, and from those in the frenotomy service to maintain masking as far as possible. Support workers will be advised to urgently re-refer infants participating in the trial who have ongoing feeding difficulties to the hospital infant feeding service for further assessment in order to minimise the chance of parents seeking frenotomy with a private provider. Staff in the infant feeding service will offer breastfeeding support to any mothers referred back with the aim of avoiding frenotomy or repeat frenotomy. However, babies with ongoing problems may be re-referred to the frenotomy service for a first or repeat frenotomy in the event that this is felt to be clinically indicated.

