9.6.2. Routine follow-up visit

The following data will be collected from the mother at the routine follow-up visit (approximately one week post-intervention according to hospital practice):

- Mother's pain while feeding during the previous 24 hours: measured using visual analogue scale
 of the Short Form McGill Pain Questionnaire (SF-MPQ), modified into a Likert-type scale (scores
 ranging from 0 to 10) (Dennis, Jackson et al. 2014)
- Exclusive breastmilk feeding in the previous 24 hours
- Exclusive breastfeeding directly from the breast with no bottle feeds of expressed milk in the previous 24 hours
- Request for frenotomy/repeat frenotomy (defined as any further procedure on tongue-tie)
- Bleeding following frenotomy or frenulum tear
- Post-procedure adverse events (tongue cut, salivary duct damage): measured by specific questions
- Maternal anxiety or depression as indicated by the anxiety and depression dimension of EQ-5D-5L
- Maternal health-related quality of life: as elicited by the EQ-5D-5L

9.6.3. 3 month follow-up

The following data will be collected using maternal self-report (by smart-phone, tablet, computer, postal questionnaire or telephone) when the infant is 3 months of age:

- Mother's breastfeeding self-efficacy: measured using the Breastfeeding Self-Efficacy Scale Short Form (Dennis 2003)
- Mother's pain while feeding during the previous 24 hours: measured using visual analogue scale
 of the Short Form McGill Pain Questionnaire (SF-MPQ), modified into a Likert-type scale (scores
 ranging from 0 to 10) (Dennis, Jackson et al. 2014)

 Total number of contacts with any breastfeeding supporter since first referral and specific means of support used

- Infant weight
- Exclusive breastmilk feeding in the previous 24 hours
- Exclusive breastfeeding directly from the breast with no bottle feeds of expressed milk in the previous 24 hours
- Age when child last received breastmilk, to determine when and whether switch to exclusive formula feeding has occurred (McAndrew, Thompson et al. 2010)
- Time spent breastfeeding in previous 24 hours: time in minutes/hours
- Request for frenotomy/repeat frenotomy
- Bleeding following frenotomy or frenulum tear
- Post-procedure adverse events (tongue cut, scarring, salivary duct damage): measured by specific questions
- Maternal anxiety or depression as indicated by the anxiety and depression dimension of EQ-5D-5L
 Maternal health-related quality of life: as elicited by the EQ-5D-5L

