11.3. Foreseeable serious adverse events

The following are known, but rare, complications of frenotomy. If they occur, they are to be reported as SAEs:

- excessive bleeding from the incision site (a small amount of bleeding is expected)
- significant soft tissue injury such as submandibular orifice injury
- severe infection

There are also SAEs which may be expected in the trial population or as a result of their routine care. The following events therefore are foreseeable SAEs and will not be subject to SAE reporting procedures:

- · admission or extension of hospital stay due to:
 - o breastfeeding difficulties
 - o poor milk supply in the mother
 - o weight less or poor weight gain in the baby
 - o laundice

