15.7. Other ethical considerations

Parents will be asked to consent for inclusion of their infants into the trial on the basis that they will be masked to intervention allocation. Parents will therefore need to be adequately advised on how to respond in the event of post-frenotomy adverse events such as bleeding, as well as what to do in the event of ongoing feeding difficulties. In order that parents are able to rapidly seek advice in the event of post-frenotomy adverse events (in the group that undergo frenotomy) or rapidly obtain further advice in the event of ongoing feeding difficulties (both groups) with recourse to rescue frenotomy or repeat frenotomy if necessary, both groups will be provided with standard post-frenotomy advice. Only sites with rapid access via drop-in clinic or telephone advice to breastfeeding support will be included in the study, and all parents will be given an appointment for at least one follow-up visit. All research midwives taking consent from parents will be trained in how to advise parents as to their actions in the event of either adverse events or ongoing feeding problems.

In order to maintain masking, infants may be taken into a separate room, where the frenotomy will be undertaken or not. This may be upsetting to both mother and infant. However, the infant will be returned to the mother after a few minutes of separation. Mothers will be made aware of this given the option to remain with their baby but will be asked not to directly observe the trial intervention in order to maintain blinding.

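### SAE reporting closes at the first follow-up visit, so the listed complications of later rescue or repeat frenotomies fall outside it

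*Protocol*

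**What the plan says.** Four parts of the protocol's safety text bear on this, together with the two places that allow later procedures.

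- **Section 11.3** names three rare complications of frenotomy: excessive bleeding, significant soft tissue injury and severe infection. It says "If they occur, they are to be reported as SAEs" and gives no period.
- **Section 11.4** sets a cut-off for one class of event: "Unforeseeable SAEs which occur from randomisation until the first routine follow-up visit must be reported".
- **Section 11.5** opens with both classes: "Unforeseeable SAEs and the SAEs associated with frenotomy (section 11.3) must be reported immediately as soon as study staff become aware of the event". Further on it gives a general period: "SAEs will be reported from trial entry until the first routine follow-up visit", roughly one week after the intervention.
- **Appendix A** marks serious and other adverse event assessment at the intervention and at the follow-up visit, and not at 3 or 6 months.
- **Section 7** says that "babies with ongoing problems may be re-referred to the frenotomy service for a first or repeat frenotomy" if this is thought clinically indicated. **Section 15.7** describes rapid advice "with recourse to rescue frenotomy or repeat frenotomy if necessary". Neither sets a time limit.

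At 3 months, section 9.6.3 asks the mother about bleeding and, as a separate item, "Post-procedure adverse events (tongue cut, scarring, salivary duct damage): measured by specific questions". It also records hospital admissions as resource use.

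**The concern.** The reporting window is tied to the allocated procedure, but the protocol expects some frenotomies after it closes. Section 9.6.2 records requests for frenotomy or repeat frenotomy at the very visit that ends the window, and section 7 has staff offer more breastfeeding support before re-referral. A procedure that follows such a request will normally fall after the cut-off.

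At stake is how serious complications of comparator-arm rescue procedures and intervention-arm repeat procedures are handled. Under the general window they receive no SAE form and no causality assessment. Because section 11.3 is silent on period and section 11.4 limits only the other class, sites could also apply different rules to the same event.

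**Working it through.** **Step 1. Set the texts side by side for a listed complication of a frenotomy done after the first follow-up visit.**

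| Text | What it fixes | Period |
|---|---|---|
| 11.3 | The event is an SAE | None given |
| 11.4 | Cut-off for unforeseeable SAEs | To first follow-up visit; this event is not in that class |
| 11.5, opening | Speed of reporting, both classes | None given |
| 11.5, later sentence | Period for SAEs in general | To first follow-up visit |
| Appendix A | When SAE assessment takes place | Intervention and follow-up visit only |

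One coherent reading exists. Section 11.3 classifies, the opening of 11.5 sets speed, and the later sentence of 11.5 with Appendix A sets the period. On that reading the event is not reportable as an SAE. The other reading is still open to a site: if the general window already covered both classes, a separate limit in 11.4 for one class would be unnecessary.

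**Step 2. What is caught elsewhere.** The 3-month questions cover bleeding, tongue cut, scarring and salivary duct damage in both arms, and an infection needing admission would appear under resource use. No infection question is listed. Section 11.1 exempts bleeding from adverse event reporting only when it is not excessive, so excessive bleeding is meant for the SAE route. Maternal reports do not receive the causality assessment of section 11.5.

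**Step 3. Size.** The protocol gives no figure for affected events, so there is none to reproduce.

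Inputs from the protocol: 870 infants randomised 1:1, so 870/2 = 435 per arm; contamination planned at 5% (sections 7.1 and 12.1).

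Assumptions, not in the protocol: listed complications in 0.5–2% of procedures; repeat frenotomy in 1–5% of the intervention arm, all after the visit; a quarter, half or all of the rescue procedures after the visit.

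Expected events = procedures after the visit × complication rate.

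- Rescue procedures: 435 × 0.05 = 21.75, about 22.
  - A quarter after the visit: 5.5 procedures; 5.5 × 0.005 = 0.03 to 5.5 × 0.02 = 0.11 events.
  - Half: 11 procedures; 0.06 to 0.22 events.
  - All: 22 procedures; 0.11 to 0.44 events.
- Repeat procedures: 435 × 0.01 = 4.35 to 435 × 0.05 = 21.75; 4.35 × 0.005 = 0.02 to 21.75 × 0.02 = 0.44 events.
- Total: (5.5 + 4.35) × 0.005 = 0.05 to (22 + 21.75) × 0.02 = 0.88 events.

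For scale, the 435 allocated frenotomies, inside the window, would give 435 × 0.005 = 2.2 to 435 × 0.02 = 8.7 events.

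**Step 4. Direction between arms, at the 2% rate.**

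- Repeats 5%, all 22 rescues after the visit: the true expectation is 8.7 + 0.44 = 9.14 vs 0.44, recorded as 8.7 vs 0. The arm difference is 8.7 both times.
- Repeats 1% (4.35 × 0.02 = 0.09), all 22 rescues after the visit: 8.79 vs 0.44 (difference 8.35) is recorded as 8.7 vs 0 (difference 8.7). The difference grows.
- Repeats 5%, a quarter of rescues after the visit: 9.14 vs 0.44 (difference 8.7) is recorded as 8.7 vs 0.33 (difference 8.37). The difference shrinks.

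The sign depends on rates that the protocol does not give.

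**The case against.** The strongest reply is that the protocol chose a window around the allocated procedure, that this is a defensible choice, and that a later frenotomy is clinical care and not the trial intervention. Most of the relevant harms are asked about at 3 months anyway, admissions are recorded, and fewer than one event is at issue. Much of this stands and keeps the point minor. It does not remove it. The later procedures run through the trial's own re-referral pathway, severe infection is one of the three listed events and has no 3-month question, and nothing replaces the causality assessment.

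Four stronger readings are tempting and are not supported.

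- **That the safety sections contradict each other.** A reader might take section 11.3 and the opening of 11.5 as an open-ended duty. The opening sentence also covers unforeseeable SAEs, which 11.4 limits to the first visit, so it cannot mean reporting without limit. The texts are ambiguous, with one coherent reading.
- **That the loss favours one arm.** Step 4 shows that the arm difference can stay the same, grow or shrink once intervention-arm repeats are counted with comparator-arm rescues.
- **That individual notification of the DMC is lost.** Section 11.5 limits that route: "If assessed to be related and unforeseeable the NPEU CTU will send the SAE report to the Sponsor and the DMC". The listed complications are foreseeable, so they would not take it in any case. Section 11 has the DMC review SAE reports more generally, so SAE status may affect what it sees there, but the protocol does not give the content of those reports.
- **That many events are affected.** Section 12.1 notes that most controls in one earlier trial had a frenotomy. This protocol plans for contamination of no more than 5%, so that trial is not a basis for sizing the gap here.

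**Conclusion.** The point holds as a gap in safety reporting with ambiguous wording. Under the general window in section 11.5, serious complications of frenotomies done after about one week lose SAE status and causality assessment, although the protocol allows those procedures and counts the same complications as SAEs when they follow the allocated one.

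The size is about 0.05 to 0.88 expected events. This rests on the protocol's 5% contamination and on the assumed complication rate, repeat rate and share of procedures after the visit. It would be zero if no procedure fell after the visit. No direction of bias between arms is established, and the primary outcome and its analysis are unaffected. It is an inexpensive improvement, and the trial's conclusions do not depend on it.

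**What to change.** In section 11.5, state that the three complications listed in section 11.3 are reportable as SAEs after any frenotomy, whether allocated, rescue or repeat, when staff become aware of them up to the 3-month follow-up. Keep the first-visit cut-off for unforeseeable SAEs as in section 11.4. Mark the change in Appendix A. Report these events by arm beside the number of frenotomies performed in each arm. If the sponsor does intend the general cut-off to cover the listed complications, section 11.3 and the opening sentence of 11.5 should say so.

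The cost is one sentence, one mark in the schedule, and a few extra SAE forms with causality assessments. No extra visit is needed. For private procedures known only from the mother's report, the causality information will be limited.

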12. STATISTICS AND ANALYSIS

12.1. Sample size

Frenotomy rates are very variable between hospitals (<1% to 6% of babies born) and evidence on which to base an estimate of effect size is very limited. The 2010 Infant Feeding Survey indicates that 68% of infants are breastfed at 6 weeks (McAndrew, Thompson et al. 2010). The current reported rate of any breastfeeding at 6-8 weeks is 4-4% (Public Health England 2016), as compared with 30% exclusive breastfeeding. Breastfeeding rates are likely to be substantially higher in the highly motivated population

eligible for this trial. Breastfeeding rates at 3 months in relatively small studies of UK babies who have undergone frenotomy have varied between 65% in Southampton (Berry, Griffiths et al. 2012) to 78% in London (Khoo, Dabbas et al. 2009). Similarly, in a Bristol trial (Emond, Ingram et al. 2014), breastfeeding rates at 8 weeks were 83% in the intervention arm and 80% in the control arm, noting that most of the control arm underwent frenotomy. Six of eight infants who did not undergo frenotomy were breastfed at 8 weeks (75%). In another Southampton trial (Hogan, Westcott et al. 2005), the breastfeeding rate at 4 months was 60% in both the immediate and delayed division groups. Audit data from the Royal Berkshire Hospital infant feeding service, which includes a frenotomy service, showed that the following proportions of infants referred to the service were exclusively breastfed at three months: 2011/12 66%, 2012/13 62%, 2013/14 61%, 2014/15 77%, 2015/16 69%.

It is assumed, as supported by public consultations, that a 10% increase in the rate of breastfeeding represents the minimal clinically important difference that should be detectable by the trial; and breastfeeding rates will remain high in this motivated population (breastfeeding rates at 3 months will be around 70% in those who receive the minimum level of breastfeeding support).

Thus assuming a breastfeeding rate of 70% in the control group and 80% in the intervention group, at 90% power with a 5% level of significance, this gives a sample size of 392 in each group, totalling 784. Allowing for 5% loss to follow-up, with a further 5% increase to account for between-group contamination would give a sample size of 870; approximately 37 infants per month over a 24 month recruitment period.

Based on an assumed 2% of infants having breastfeeding difficulties and judged to have tongue-tie, an average number of births of 3,000 per centre, and a conservative 50% of mothers consent for their infant to participate, this would require 19 participating units (representing almost 114,000 births over the study period), with an estimated 2,300 babies with breastfeeding difficulties thought to have a tongue-tie (96 babies per month). With conservative estimates that assume 1 in 2 babies will be assessed and their parents agree to participate and provide complete outcome data, sufficient numbers to achieve our goal within the 3 years of the study are expected.

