7.1. Internal pilot

The internal pilot will assess monthly recruitment, masking, loss to follow up and contamination. It will assess the following assumptions:

- Monthly recruitment of 2 infants per centre by month 6
- Centres take 2 months to reach stable recruitment
- All pilot centres actively recruiting by month 6
- Masking is effective
- Loss to follow-up overall is less than 5%
- Contamination between arms is no more than 5%
- The proportion of babies recruited at four weeks or over is less than 40%

Pre-defined stop-go criteria after 9 months, with 266 recruits predicted, will be:

- Recruitment is 75% or more (N ≥ 199) continue directly with the main trial;
- Recruitment is 50-75% (133 ≤ N < 199) recruit more centres and review in 6 months;
- Recruitment is < 50% (N < 133) undertake an urgent detailed review of options with Trial Steering Committee to subsequently recommend to the funder.

All mothers of infants recruited during the pilot phase will be asked at the three-month follow-up whether they remained masked to their infant's treatment allocation. If parents remain masked, the study will continue with the masked design, recording blinding status.

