9.4. Randomisation

The infants entered into the trial will be randomised 1:1 to either:

- frenotomy with standard breastfeeding support (intervention arm), or
- no frenotomy with standard breastfeeding support (comparator arm).

Multiples (twins or higher order multiples) will be randomised to the same arm. Stratified block randomisation (using variable block sizes) will be performed via a secure 24-hour web-based randomisation system (hosted by the NPEU CTU, University of Oxford) stratified by infant's age (<2 and ≥2 weeks) at randomisation, mother's parity (primiparous or multiparous) within centre. A telephone back-up system will be available 24 hours a day (365 days per year). Users of the system will have no insight into the next allocation.

A statistician independent of the trial at the NPEU CTU will generate the randomisation schedule and the Senior Trials Programmer will write the web-based randomisation program; both will be independently validated. The implementation of the randomisation procedure will be monitored by the Senior Trials Programmer and independent statistician throughout the trial and reports will be provided to the Data Monitoring Committee.

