12.3. Level of statistical significance

Two-sided statistical testing will be performed throughout. A 5% level of statistical significance will be used for analyses of all outcomes.

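### The 5% allowance for contamination is applied as if it were drop-out, so 870 infants give about 89% power rather than 90% at the plan's own 5% contamination

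*Protocol*

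**What the plan says.** Protocol section 12.1 sets the target "assuming a breastfeeding rate of 70% in the control group and 80% in the intervention group" and reports that "at 90% power with a 5% level of significance, this gives a sample size of 392 in each group, totalling 784". It then inflates: "Allowing for 5% loss to follow-up, with a further 5% increase to account for between-group contamination would give a sample size of 870". The direction of contamination is not defined there.

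Section 7.1 lists, among the assumptions that the internal pilot will assess, "Contamination between arms is no more than 5" per cent, and overall loss to follow-up below 5%. Section 12.2 makes the comparison by intention to treat: every infant is analysed in the arm to which it was allocated, whatever it received. Section 12.3 adds that "Two-sided statistical testing will be performed throughout". No section reduces the 10-point difference to allow for contamination.

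**The concern.** Loss to follow-up and contamination act on power in different ways. A lost infant removes information, and dividing by one minus the loss rate restores it. A comparator infant who has a frenotomy is still counted in the comparator arm and moves that arm's rate towards the intervention rate. The required number varies with the inverse square of the difference, so a linear allowance is too small.

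At stake is whether the sample size statement holds under its own assumptions. Section 12.1 presents 870 as giving 90% power with 5% contamination already covered. If the pilot observed exactly 5%, a reader would conclude that the stated power was intact. Contamination is also a foreseeable risk here: section 12.1 itself notes an earlier trial in which most control infants underwent frenotomy, and section 7 allows re-referral for a first frenotomy. The linear method falls further short as the rate rises.

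**Working it through.** **Inputs.** Rates of 70% and 80%, 90% power, 5% significance, 5% loss and 5% contamination (section 12.1); two-sided testing (section 12.3); 1:1 allocation (section 9.4); analysis as randomised (section 12.2).

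**1. Base figure.** Two proportions, pooled variance under the null, no continuity correction, with p̄ the mean of the two rates:

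n per arm = [1.960·√(2p̄(1−p̄)) + 1.2816·√(p₁(1−p₁) + p₂(1−p₂))]² / (p₂−p₁)²

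With p₁ = 0.70, p₂ = 0.80 and p̄ = 0.75: [1.960 × 0.6124 + 1.2816 × 0.6083]² / 0.01 = 391.9, so 392 per arm and 784 in all. This matches the protocol.

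**2. Inflation.** 784/0.95/0.95 = 868.7, and 784/0.90 = 871.1. Either gives 870 after rounding. Both are linear, so contamination received the same kind of factor as loss, about 1/0.95 = 1.053.

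**3. Factor needed under intention to treat.** If a share c of the comparator arm takes the intervention-arm rate, the difference becomes (1−c) × 10 points and the number grows by about 1/(1−c)². At c = 0.05 this is 1/0.95² = 1.108.

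**4. Direct calculation at 5% in the comparator arm.** The comparator rate becomes 0.70 + 0.05 × 0.10 = 0.705, against 0.80, a difference of 9.5 points. The formula in step 1 gives 431.6 per arm, or 863.2 analysed. Dividing by 0.95 for loss gives about 909 randomised, 4.5% above 870.

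**5. Power of 870.** After 5% loss, 870 × 0.95 = 826.5 are analysed, or 413.25 per arm.

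Power = Φ{[(p₂−p₁)√n − 1.960·√(2p̄(1−p̄))] / √(p₁(1−p₁) + p₂(1−p₂))}

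For 0.705 versus 0.80: (1.9312 − 1.960 × 0.6103)/0.6066 = 1.212, so power is 88.7%.

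| Comparator infants crossing over | Rates | Power, 870 randomised and 5% lost |
|---|---|---|
| 0% | 70.0% vs 80% | 91.4% |
| 2.8% | 70.28% vs 80% | 90.0% |
| 5% | 70.5% vs 80% | 88.7% |
| 10% | 71.0% vs 80% | 85.4% |

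So 870 holds 90% power up to about 2.8% contamination when 5% are lost.

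**6. Sensitivity of the result.**
- No loss at all and 5% crossover (435 per arm): 90.2%. The total covers this contamination or 5% loss, but not both.
- Crossovers gain half the benefit (70.25% vs 80%): 90.2%. Three quarters (70.375% vs 80%): 89.5%.
- 5% contamination in total, split evenly between the arms (70.25% vs 79.75%): 88.5%.
- 5% crossover in each arm (70.5% vs 79.5%): 84.9%, with about 1,020 needed.

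**The case against.** The strongest reply is that the gap is too small to matter. It is 1.3 power points, and uncertainty in the assumed control rate moves power by as much: with 826 analysed, 65% versus 75% gives 88.2% and 72% versus 82% gives 92.9%. Both 5% figures are ceilings in section 7.1, and the shortfall appears only when loss and contamination are both near them. The calculation gives each crossover the full intervention-arm rate, yet section 7 describes a first frenotomy in the comparator arm as a later step, after re-referral and further support; at half benefit the stated 90% holds. The primary analysis is adjusted for centre, age and parity, and a variance reduction of about 4% would close the gap. Nor does any decision rule depend on the figure, since the stop-go criteria concern recruitment only.

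Most of this stands, and it limits the size of the point. It does not rescue the method. Section 12.1 says that the increase accounts for contamination, and on its own 5% and 5%, with crossovers taking the full rate, it does not. The protocol gives no reduced benefit for crossovers and no expected gain from adjustment.

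A reader might infer from the phrase about contamination between groups that 5% cross over in each arm, and so that power is only about 85% with some 1,020 infants needed. The documents do not establish this. Where the protocol describes crossover, it means frenotomy in the comparator arm: section 7 speaks of limiting recourse to private frenotomy there, and section 6 lists frenotomy in that group as an outcome. No listed outcome records an allocated frenotomy that was not done.

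**Conclusion.** The point holds as a small error of method. Section 12.1 treats contamination as lost numbers when, under intention to treat, it dilutes the difference. With 5% lost and 5% of comparator infants crossing over, 870 gives about 88.7% power instead of 90%, and about 909 would restore it.

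The result rests on three assumptions: 70% and 80% are the rates without contamination, as adding an allowance for it implies; crossovers take the full intervention-arm rate; and adjustment for the stratification factors adds no precision. It does not show that the trial is materially underpowered. The figure of about 85% for 5% crossover in each arm is a worst case only.

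**What to change.** Keep 870. In section 12.1, state which direction of contamination is meant, and replace the claim that a 5% increase accounts for it with wording such as:

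*870 infants, allowing 5% loss to follow-up, give about 91% power with no contamination, about 89% if 5% of the comparator arm cross over and about 85% if 10% do, assuming crossovers take the full intervention-arm rate.*

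If 5% crossover in each arm is mentioned (also about 85%), label it as a worst case that the protocol does not assume.

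The cost is a change of wording in one section and a slightly less favourable power statement. No extra infants are needed, and neither the design nor the analysis changes.
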